13.1 Exposure Calculation

Exposure for 52-week treatment period will be presented for PA, whereas exposure for LTE period and overall exposure will be presented for LTE analysis.

Dose interruptions/changes will not be considered in exposure calculation. Dose interruptions/changes with the associated reason will only be listed.

PA: 52-week treatment period

[figure not shown]
Details describing study therapy dosing and administration are provided in [Table 16](#).

Table 16 : Dosage and Administration of Investigational Medicinal Product

Product Description	Dosage Form	Evobrutinib Dose	Number of Tablets (Morning Dose)		Number of Tablets (Evening Dose)	
			25 mg		25 mg	
			Evobrutinib	Placebo	Evobrutinib	Placebo
Evobrutinib	Oral	25 mg QD	1	2	0	2
Evobrutinib	Oral	75 mg QD	3	0	0	2
Evobrutinib	Oral	50 mg BID	2	1	2	0
Placebo	Oral	0 mg	0	3	0	2

BID – Twice Daily; QD – Once Daily.

Treatment duration in weeks will be calculated according to the following formula:

$$\text{Treatment duration (weeks)} = \frac{(\text{date of last dose} - \text{date of first dose} + 1)}{7}$$

First dose refers to the first administration of any IMP in 52-week treatment period. Last dose refers to the last administration of any IMP in 52-week treatment period. Both dates of first and last dose will be retrieved from SDTM EC domain.

Treatment duration will be presented by summary statistics and according to the following categories:

- ≤ 1 week
- > 1 to 8 weeks
- > 8 to 16 weeks
- > 16 to 24 weeks
- > 24 to 32 weeks
- > 32 to 40 weeks
- > 40 to 48 weeks
- > 48 to 52 weeks
- > 52 weeks

The calculated total dose (mg) per subject for the 52-week treatment period will also be summarized for the active treatment groups, based on the actual treatment the subject receives. The calculated total dose is defined according to the following formula:

$$\text{Calculated total dose (mg)} = \text{Treatment duration} \times \text{Daily dose}$$

where the exposure time is expressed in days and the daily dose is provided in [Table 16](#).

The cumulative actual dose (mg) per subject for the 52-week treatment period will also be summarized for the active treatment groups. The cumulative actual dose is defined according to the following formula:

$$\text{Cumulative actual dose (mg)} = \text{Number of tablets ingested} \times Fr \times 25\text{mg}$$

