where the number of tablets ingested is defined below, and Fr is the fraction of tablets that contain evobrutinib 25 mg according to the actual treatment group:

$$Fr = 0 \text{ for Placebo}$$

$$Fr = \frac{1}{5} \text{ for Evobrutinib 25 mg QD}$$

$$Fr = \frac{3}{5} \text{ for Evobrutinib 75 mg QD}$$

$$Fr = \frac{4}{5} \text{ for Evobrutinib 50 mg BID}$$

The number of ingested tablets will be retrieved from the BATCH (Study Treatment Box Number) panel of the CRF, the number of tablets dispensed being equal to 170 for a given kit during the treatment period and 32 during the LTE period:

$$\text{Number of tablets ingested} = \text{Number of tablets dispensed} - \text{number of tablets returned}$$

Cumulative actual dose cannot be calculated for placebo treatment group.

For subjects with missing number of tablets returned (e.g. lost to follow-up), the cumulative actual dose will be calculated by imputing the missing returned amount with the number of tablets the subjects should have returned if 100% compliance was observed while on treatment for the associated dispensed kit.

Example: Let's consider a subject that has been exposed to study drug for 90 days before withdrawal and assigned to Evobrutinib 50 mg BID group. The subject has received 3 kits of tablets (170 tablets each) and returned 10 tablets for the 1st kit, 12 for each of the two other kits. The number of tablets ingested is calculated as $170 * 3 - (10 + 12 + 12) = 476$. The calculated total dose is equal to $90 * 100 = 9000$ mg and the cumulative actual dose is equal to $476 * 4/5 * 25 = 9520$ mg.

LTE Analysis: LTE period

Treatment duration in months in the LTE period will be calculated according to the following formula:

$$\text{Treatment duration (months)} = \frac{(\text{date of last dose} - \text{date of first dose} + 1)}{30.4375}$$

First dose refers to the first administration of evobrutinib 50mg BID in LTE period.

Treatment duration will be presented by summary statistics and according to the following categories:

- ≤ 4 months
- > 4 to 8 months
- > 8 to 12 months
- > 12 to 16 months
- > 16 to 20 months
- > 20 to 24 months
- > 24 months

The calculated total dose and cumulative actual dose (mg) per subject for the LTE period will also be summarized, defined as for the 52-week treatment period. As all subjects will be receiving evobrutinib 50mg BID in the LTE period, cumulative actual dose will be calculated using:

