$$\text{Cumulative actual dose (mg)} = \text{Number of tablets ingested} \times 25\text{mg}$$

LTE analysis: Overall period (i.e. 52-week treatment period + LTE)

Overall exposure will be presented on LTE SAF only for subjects who received evobrutinib 50 mg BID during the 52-week treatment period and continue with the same dose of evobrutinib during LTE period.

Treatment duration in months will be calculated according to the following formula:

$$\text{Treatment duration (months)} = \frac{(\text{date of last dose} - \text{date of first dose} + 1)}{30.4375}$$

First dose refers to the first administration of evobrutinib 50mg BID in the study (i.e. first dose in the 52-week treatment period). For subjects with a gap greater than or equal to 2 weeks between the 52-week treatment period and LTE treatment period, the treatment duration will be derived by adding the 52-week treatment duration and the LTE treatment duration, both calculated separately.

Treatment duration will be presented by summary statistics and according to the following categories:

- ≤ 6 months
- > 6 to 12 months
- > 12 to 18 months
- > 18 to 24 months
- > 24 to 30 months
- > 30 to 36 months
- > 36 months

The calculated total dose and cumulative actual dose (mg) per subject will be computed as well, defined as for the LTE period.

Subject data listings:

Study drug administrations will also be listed by treatment group, and subject, with start/end dates of administration and reason for dose change (if applicable).

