13.2 Compliance Calculation

Compliance will be separately analyzed for the PA and LTE analysis, in the same manner as exposure was analyzed.

PA: 52-week treatment period

For the 52-week treatment period, compliance with treatment is defined as the number of tablets taken during a period divided by the number of tablets that should have been taken during that period, multiplied by 100 to yield a percentage, i.e.:

$$\text{Compliance with treatment} = 100 \times \left(\frac{N_1}{5 \times N_2} \right)$$

where

- N_1 = number of tablets given minus number of tablets returned over N_2 days,
- N_2 = number of days between treatment start and treatment termination visit,

where N_1 will be computed using the BATCH form of the eCRF and N_2 corresponds to the exposure time expressed in days (see Section 13.1 for exposure time and number of tablets ingested formulas).

For the 52-week treatment period, the last kit dispensed is at Week 48 visit. The number of tablets returned for this last kit is entered during Week 52 visit.

Example: Let's consider the example from Section 13.1. The subject has been provided with 510 tablets, returned 34 tablets and has been exposed to study drug for 90 days. Therefore, N_1 is

equal to $510 - 34 = 476$ and N_2 is equal to 90, which gives a compliance equal to $100 * (476 / 5*90) = 105.8\%$.

For subjects with missing number of tablets returned (e.g. lost to follow-up), the compliance will be calculated by imputing the missing returned amount with the number of tablets the subjects should have returned if 100% compliance was observed while on treatment for the associated dispensed kit.

Compliance with treatment will be tabulated by treatment group from first intake to last intake of 52-week treatment period.

Compliance with treatment will also be presented into categories as follows:

- $< 60\%$
- $\geq 60\%$ to $< 80\%$
- $\geq 80\%$ to $\leq 100\%$
- $> 100\%$ to $\leq 110\%$
- $> 110\%$

LTE analysis: LTE period

Compliance for the LTE period will be presented on subjects from LTE SAF.

For the LTE period, compliance with treatment is defined using the formula below (4 tablets taken per day, 2 in the morning and 2 in the afternoon):

$$\text{Compliance with treatment} = 100 \times \left(\frac{N_1}{4 \times N_2} \right)$$

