The compliance will be computed using the number of kits dispensed as well as the number of tablets returned. Compliance with treatment will be tabulated by treatment group from first intake in LTE to last intake during LTE period and also presented within categories, as for the 52-week treatment period.

The first kit dispensed in LTE treatment period is at Week 52 visit for subjects who rolled over directly from 52-week treatment to LTE.

LTE analysis: Overall period (i.e. 52-week treatment period + LTE)

Overall compliance will be presented on LTE SAF only on subjects who received evobrutinib 50 mg BID during the 52-week treatment period and continue with the same dose of evobrutinib during LTE period.

Overall compliance with treatment is defined using the formula below:

$$\text{Compliance with treatment} = 100 \times \left[\left(\frac{N_1}{5 \times N_2} \right) + \left(\frac{N_3}{4 \times N_4} \right) \right] / 2$$

where

- N_1 = number of tablets given minus number of tablets returned over N_2 days for the 52-week treatment period
- N_2 = number of days between treatment start and treatment termination visit for the 52-week treatment period
- N_3 = number of tablets given minus number of tablets returned over N_2 days for the LTE treatment period
- N_4 = number of days between treatment start and treatment termination visit for the LTE treatment period

Compliance with treatment will be tabulated from first intake to last intake of the study and also presented within categories, as for the 52-week treatment period.

Subject data listings:

For each analysis, the following listings will be provided:

- listing of kit numbers with date of dispense, and number of tablets returned (from BATCH).
- listing of start/end dates with number ingested tablets (from EXPOSUREDT).
- listing with exposure time, cumulative dose, and compliance.

14 Endpoint Evaluation

For all efficacy endpoints:

- Analysis visits will be used (as detailed in Section 9.7 and Appendix 18.11).
- Baseline definition from Section 9.5 should be applied.
- Statistical tests of the two-primary and key secondary efficacy endpoints entering the hierarchical testing procedure (see section 14.1.2.4) will be conducted at a one-sided α level of 0.025. The one-sided p-values and the two-sided 95% CIs will be presented as well as a note on how to interpret correctly the two-sided 95% CIs by considering appropriately the accurate boundary of the interval.

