15.1.1 All Adverse Events

AEs will be coded according to the latest MedDRA version available at the time of analysis. The severity of AEs will be graded using NCI-CTCAE version 4.03 toxicity grades. AEs with missing classification concerning IMP relationship will be considered related to the IMP.

15.1.1.1 3-Tier Approach

The 3-tier approach is a systematic way to summarize and analyze adverse events (AEs) in clinical trials (Crowe 2009). AEs in different tiers are analyzed using different levels of statistical analyses.

3-Tier approach will be used for PA only.

The AEs identified by the Benefit Risk Action Team for Tier 1 reporting in this trial are in [Table 27](#).

Table 27: Tier 1 AEs

Tier 1 AE (PT)	Within group summary	Between group comparison (Evobrutinib - Placebo) 95% CI
Transaminases elevations Alanine aminotransferase abnormal Alanine aminotransferase increased Aspartate aminotransferase abnormal Aspartate aminotransferase increased Hypertransaminasaemia Transaminases abnormal Transaminases increased	n (%)	Δ [xx%, xx%]

Tier 1 AE will be identified using sponsor-defined list of search term as defined in [Table 27](#) (refer to Appendix 18.14).

All AEs will be further classified into Tier 2 or Tier 3 based on the Rule-of-3. If there are 3 or more subjects with the reported term in any treatment group, that term will be included in Tier 2. Otherwise, it will be included in Tier 3.

The Tier 1 and Tier 2 AEs will be assessed with a 95% CI for between-group comparisons. For the difference in crude rates, the CIs will be based on MN method ([Miettinen 1985](#)).

Exposure Adjusted Incidence Rate (EAIR) of TEAEs will also be separately presented for each Tier, by SOC and PT (see Section 15.1.1.3 for multiple events handling). For this trial, difference in EAIR will also be summarized. For Tier 1 and Tier 2 AEs, the CIs will be calculated using a Poisson binomial model. An example of SAS code is available in Appendix 18.9.

No multiplicity adjustment will be applied for Tier 1 and 2 AEs. The Tier 3 AEs will be assessed via summary statistics and risk differences.

For each comparison of evobrutinib group with placebo, forest trees for Tier 1 and Tier 2 AEs will be provided as well, displaying the incidence rate and associated 95% CI of difference.

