18.9.4 EAIR of TEAEs: computation of Tier 1 and Tier 2 95% CIs

95%CI of the incidence rate will be computed using the GENMOD procedure from SAS ® with lsmeans instruction using a Poisson binomial model as follows:

```
ods listing close;
  proc genmod data=<Dataset>;
    where rate > 0;
    by <SOC/PT>;
    class <TreatmentGroup>;
    model rate = <TreatmentGroup> / dist=poisson link=log
    offset=log(PatientYears/1000);
    lsmeans <TreatmentGroup> / ilink cl;
    ods output lsmeans=OutLSmeans;
run;
ods listing;
```

[figure not shown]
where

<TreatmentGroup> represents the treatment group variable (usually TRT01AN)
<SOC/PT> represents the sorting variable (label for Overall, by SOC and by PT within SOC).

The 95%CI of difference with Placebo will be computed using MN method as follows:

```
proc freq data=<Dataset>;
  tables TreatmentGroup *AVALC / out=<outDataset> RISKDIFF (CL=MN) alpha=0.05;
  by AESOC AEDECOD;
  ods output PdiffCLs=<outPdiffCLs >;
run;
```

[figure not shown]
CCI

[figure not shown]
CCI

[figure not shown]
CCI

[figure not shown]
CCI

CCI

[figure not shown]
CCI

[figure not shown]
CCI

[figure not shown]
CCI

CCI

CCI

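### Overall cumulative actual dose counts placebo tablets as drug, overall compliance averages periods of unequal length, and the EAIR sample code needs its response, zero-event filter and difference interval fixed

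*SAP*

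**What the plan says.** **Dose (section 13.1).** Table 16 gives the blinded 50 mg BID arm three morning and two evening tablets: "Evobrutinib Oral 50 mg BID 2 1 2 0", that is, four active and one placebo. For the 52-week period, cumulative actual dose is tablets ingested × Fr × 25 mg, where "Fr is the fraction of tablets that contain evobrutinib 25 mg according to the actual treatment group"; Fr is 4/5 for this arm. In the LTE every tablet is active, so Fr is dropped. The overall period is reported only for subjects who took 50 mg BID in the 52-week period and continued on it, and there the SAP states: "The calculated total dose and cumulative actual dose (mg) per subject will be computed as well, defined as for the LTE period".

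**Compliance (section 13.2).** The rule given for the first 52 weeks is this: "compliance with treatment is defined as the number of tablets taken during a period divided by the number of tablets that should have been taken", expressed as a percentage, with 5 tablets due per day. The LTE uses the same ratio with 4 per day. The combined period has its own rule: "Overall compliance with treatment is defined using the formula below", namely 100 × [N1/(5×N2) + N3/(4×N4)] / 2. N3, the LTE tablet count, is described as counted over N2 days, although N2 is the length of the 52-week period and N4 that of the LTE.

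**EAIR (sections 15.1.1 and 18.9.4).** Section 15.1.1.3 defines EAIR as subjects with the event divided by summed exposure time. Section 15.1.1.1 assigns the Miettinen–Nurminen (MN) interval to crude differences and a Poisson-type model to EAIR intervals, and adds: "For this trial, difference in EAIR will also be summarized". The sample code has "model rate = <TreatmentGroup> / dist=poisson link=log" with an offset of log(PatientYears/1000) and the filter `where rate > 0`. Its only difference interval is MN on a treatment-by-event table.

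**The concern.** The overall dose rule borrows the one formula that has no placebo correction, and applies it to the subjects whose first year included a daily placebo tablet. The overall compliance rule gives a short LTE the same weight as a full year. LTE lengths will vary because a two-year extension was cut short by termination of the study. In the EAIR code, a response that really is a rate would be divided by exposure a second time by the offset. The filter drops arms without events. The MN interval on crude proportions does not describe a difference in exposure-adjusted rates.

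At stake are the reported dose and compliance on continuous 50 mg BID, and the EAIR intervals for Tier 1 (transaminase) and Tier 2 terms. No efficacy test uses any of these.

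**Working it through.** **The plan's own example.** Three kits of 170 tablets less 34 returned: 510 − 34 = 476 tablets over 90 days. Calculated total dose: 90 × 100 = 9,000 mg. Cumulative actual dose: 476 × 4/5 × 25 = 9,520 mg. Compliance: 100 × 476/(5 × 90) = 105.8%. All agree with the SAP. Without Fr, the same subject would show 476 × 25 = 11,900 mg, or 25% more.

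**1. Overall cumulative actual dose.** Take full compliance and 364 days in the first period, so 364 × 5 = 1,820 tablets. As written, these count as 1,820 × 25 = 45,500 mg. With Fr they count as 1,820 × 4/5 × 25 = 36,400 mg. The excess is 364 placebo tablets × 25 mg = 9,100 mg. Each LTE day adds 4 × 25 = 100 mg under either rule. LTE days are assumptions:

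| LTE days | As written (mg) | With Fr on 52-week tablets (mg) | Excess |
|---|---|---|---|
| 28 | 48,300 | 39,200 | 23.2% |
| 84 | 53,900 | 44,800 | 20.3% |
| 364 | 81,900 | 72,800 | 12.5% |
| 730 | 118,500 | 109,400 | 8.3% |

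Internal check: calculated total dose for 364 + 28 days is 392 × 100 = 39,200 mg. That equals the corrected cumulative dose, as it should at full compliance, and not the 48,300 mg from the rule as written.

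**2. Overall compliance.** Compare the plain mean with tablets taken over tablets due, 100 × (N1 + N3)/(5×N2 + 4×N4). The compliance values and LTE lengths are assumptions.
- 95% over 364 days and 50% over 28 LTE days: the mean is 72.5%. Pooled: (0.95 × 1,820 + 0.50 × 112)/(1,820 + 112) = 1,785/1,932 = 92.4%.
- 60% over 364 days and 95% over 730 LTE days: the mean is 77.5%. Pooled: (0.60 × 1,820 + 0.95 × 2,920)/(1,820 + 2,920) = 3,866/4,740 = 81.6%.
- 95% in both periods: both rules give 95%.

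The first two cases cross the 80% boundary of the SAP's reporting categories. The rules differ only when both compliance and tablets due differ between the periods.

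**3. EAIR code.** Assume one arm with 10 subjects with the event in 100 patient-years, so the true EAIR is 100 per 1000 patient-years. With a response y and this offset, the estimate is y/(100/1000) and the 95% limits are that estimate × exp(±1.96/√y).
- y = 10 (count): 100 (54 to 186), which is correct.
- y = 100 (rate per 1000 patient-years): 1000 (822 to 1217).
- y = 0.1 (rate per patient-year): 1.0 (0.002 to 492).

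So the code is right for a count and wrong for either rate. The filter matters whichever variable is used: a term enters Tier 2 with 3 subjects in any one group, so another arm, placebo included, can have none. Such an arm has an EAIR of 0 but gets no interval. An exact Poisson upper limit exists: −ln(0.025) = 3.69 events, or 36.9 per 1000 patient-years on an assumed 100 patient-years.

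**The case against.** **Dose.** The sentence in section 13.1 covers two measures, and a reader might infer that both are wrong. They are not: calculated total dose is days × daily dose and uses no tablet count. Nor does the 25% describe any reported overall figure, because every subject in that summary also has LTE exposure. For many the excess will be smaller. A subject randomized on the cohort cut-off of 28 November 2018 who rolled over directly after 364 days would have had about 117 LTE days by the announcement on 23 March 2020. The excess would then be 9,100/(36,400 + 11,700) = 18.9%. This limits the size but does not remove the error.

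**Compliance.** The tablets-taken-over-tablets-due definition is introduced for the 52-week period, and the combined period has its own explicit formula. A reader might call this a direct contradiction; it is a departure from the same principle. Each period's compliance is also tabulated separately, and the two rules agree when compliance is similar. The N2 in the definition of N3 is a subscript slip whose intent is clear. All of that stands, but the combined figure is still not the share of due tablets that was taken.

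**EAIR.** The code is labelled an example, and the main text defines EAIR correctly. A reader might infer that the rates are certainly divided by exposure twice, or that the intervals are certainly too narrow. The document supports neither. The variable `rate` is never defined; a count gives the right answer, and the direction of the interval error depends on the unit of a rate. That the filter would delete every event-free subject likewise holds only if the data are one row per subject. A log-link model has no finite estimate for an arm with no events, so some special handling is needed. The main text already keeps MN for crude rates, and the reference list includes a paper on intervals for an EAIR difference. What remains is the undefined response, the unhandled zero-event arm, and the absence from section 18.9.4 of any interval for the EAIR difference.

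**Conclusion.** The point holds for descriptive exposure and safety outputs only.

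- **Cumulative actual dose, overall period:** wrong as written. The 52-week part is overstated by 25% (9,100 mg over 364 days at full compliance), and the overall figure by about 8% to 23% for assumed LTE durations of 730 down to 28 days.
- **Overall compliance:** a poor summary when period lengths and compliance differ. It can move a subject across the 80% boundary in either direction's example above, but those compliance values are assumed, so how often this happens is unknown.
- **EAIR code:** double division by exposure is conditional on what `rate` holds. The zero-rate filter and the missing EAIR-difference interval stand without that condition.

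Nothing here bears on the two-primary or key secondary analyses.

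**What to change.** - **Section 13.1, overall period:** cumulative actual dose = 25 mg × (4/5 × tablets ingested in the 52-week period + tablets ingested in the LTE). Leave calculated total dose unchanged.
- **Section 13.2, overall period:** compliance = 100 × (N1 + N3)/(5×N2 + 4×N4), with N3 counted over N4 days.
- **Section 18.9.4:** state that the Poisson response is the number of subjects with the event, with offset log(patient-years/1000). Remove `where rate > 0`, keep zero-event arms and give them exact Poisson limits. Specify an interval for the EAIR difference, such as a score interval, and keep MN for the crude difference only, as section 15.1.1.1 already provides.

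The first two are formula edits to LTE-analysis summaries and need no new data. The tier intervals belong to the primary analysis, whose results had been reviewed before this SAP version. For those, check which variable the production program used, and rerun the affected tables if it was a rate, if zero-event arms were dropped, or if the MN interval was reported as the EAIR difference.
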